14.2 Statistical Analysis

Primary outcome measure: change in skeletal muscle microvascular blood flow during regadenoson infusion, obtained at baseline and at end of infusion (24 hours); Secondary outcome measures: myocardial microvascular blood flow, functional microvascular density, reduction in iNKT cell activity (as measured by phospho-NF-kB expression).

We anticipate that at baseline sickle cell disease subjects will have skeletal muscle blood flow similar to that of subjects with diabetes who are hyperemic, for whom data suggests a mean blood flow of 0.7 (standard deviation 0.3) ³⁰. We seek to detect a 30% increase from baseline in skeletal muscle microvascular blood flow, to a mean of 1.0, following the administration of regadenoson (Aim 1). With 27 patients enrolled on the 24 hour regadenoson study of Aim 1, we will have 90% power to

detect this difference, testing at the one-sided 0.05 significance level. For these calculations we assume that the unknown correlation of measurements within patient is positive, and that therefore the maximum value for the variance of the difference will be two times the variance of a single observation, or 0.18 (standard deviation 0.42). Secondary outcome measures will be summarized and differences assessed for regadenoson therapy, and tested with the one-sample t-test if symmetry holds and the Wilcoxon signed rank test if it does not. Serial measures of iNKT cell number and activation state and markers of inflammation will be obtained during therapy. We will construct longitudinal mixed models of these outcomes, controlling for demographic factors.

Since we do not know the magnitude of complement deposition on the lipid microbubbles in this setting, power calculations will use the Wilcoxon rank sum test, assessing number of standard deviations of difference. We will have 87% power to detect a 1.5 standard deviation difference and 80% power to detect a 1 standard deviation difference in complement deposition between the subjects who did and did not have reactions, testing at the 0.10 one-sided significance level.

References

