9.7 Exploratory Study of complement deposition on Definity microbubbles in vivo (optional)

Complement deposition on the surface of lipid microbubbles will be compared between samples collected in subjects with SCD who had pain events associated with Definity (n=4), patients SCD who did not have a pain event (n=10) and healthy African American controls (n=10). We will collect up to 4ml whole blood into anticoagulated tubes, and spin for plasma, transfer to anonymized cryovials, and store at -80C until ready for analysis. Samples will be analyzed at the laboratory of [name] in Portland, OR.

In [name] laboratory in Portland, plasma will be incubated with lipid microbubbles and then flow cytometry will be performed to measure surface complement deposition on the microbubbles. Approximately 4ml blood will also be collected for isolation of serum and analyzed for levels of circulating complement (C3, C4, CH50) at a clinical laboratory.

10. Subject Remuneration

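### The 80% power stated for a 1 SD difference in complement deposition is about 60% for 4 reactors against 10 non-reactors (normal shift)

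*Combined protocol and SAP*

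**What the plan says.** Section 14.2 says the size of complement deposition in this setting is unknown, so "power calculations will use the Wilcoxon rank sum test, assessing number of standard deviations of difference". It then states: "We will have 87% power to detect a 1.5 standard deviation difference and 80% power to detect a 1 standard deviation difference". The sentence goes on to attach both figures to a difference "in complement deposition between the subjects who did and did not have reactions, testing at the 0.10 one-sided significance level". That is one comparison, one test and one significance level for both powers.

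Section 9.7 gives the group sizes: "subjects with SCD who had pain events associated with Definity (n=4") and "patients SCD who did not have a pain event (n=10) and healthy African American controls (n=10"). The blood-sample subsection at the end of Section 4 caps collection at 14 SCD subjects, which equals 4 + 10, and 10 healthy controls. No other group size is attached to either power figure.

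Complement deposition is the first-listed secondary objective (Section 2.2) and the first-listed secondary endpoint (Section 14.1.2).

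**The concern.** The two powers do not look compatible. If a comparison has 87% power at 1.5 SD, cutting the difference by a third should cost far more than 7 points. With only 4 subjects in the smaller group, 80% power at 1 SD is also implausibly high.

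What is at stake is how a negative result would be read. The substudy asks whether complement explains the pain reactions to Definity seen in SCD patients. A null finding believed to have 80% power at 1 SD would count as fair evidence against a difference of that size. If the power is nearer 60%, the same finding says much less, and the mechanism could be discounted too readily.

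**Working it through.** **Inputs**
- Test: Wilcoxon rank sum, one-sided α = 0.10 (Section 14.2).
- Differences: d = 1.5 and d = 1, in SD units (Section 14.2).
- Groups: m = 4 reactors, n = 10 non-reactors (Section 9.7).
- Assumed here, because the plan names no distribution: normal data, equal SDs, pure shift.

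**Methods**
- Exact rank sum. Reject when U ≥ 30 of a possible 40. The true size is 0.094; the next cut-off, U ≥ 29, would have size 0.120. Power by simulation, with 200,000 or more replicates.
- Noncentral t: δ = d·√(mn/(m+n)), m+n−2 = 12 degrees of freedom, critical value 1.356. This is the normal-theory benchmark for the rank test.
- Efficiency-adjusted t: the same with δ multiplied by √(3/π) = 0.977, a usual approximation for the rank sum test.

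**Step 1: reproduce the 87% at 1.5 SD.** √(40/14) = 1.690, so δ = 1.5 × 1.690 = 2.535.
- Exact rank sum: 84.8%
- Efficiency-adjusted t: 86.6%
- t-test: 87.8%

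The stated 87% is recovered, which supports 4 against 10 at one-sided 0.10 as the inputs used.

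**Step 2: the same inputs at 1 SD.** δ = 1.690.
- Exact rank sum: 59.8%
- Efficiency-adjusted t: 62.3%
- t-test: 63.7%

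The stated 80% is not recovered. The gap is 80 − 63.7 = 16.3 points (t-test) to 80 − 59.8 = 20.2 points (exact). Noether's formula agrees: P(X>Y) = Φ(1/√2) = 0.760, and Φ(√(12·40/14) × 0.260 − 1.282) = Φ(0.242) = 59.6%.

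**Step 3: other readings that might give 80%**

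| Reading | Power at 1 SD | Power at 1.5 SD |
|---|---|---|
| Stated in the plan | 80% | 87% |
| 4 vs 10, α 0.10 | 60–64% | 85–88% |
| 4 vs 20 (healthy controls pooled with non-reactors) | 65% exact, 68% adjusted t, 69.5% t | 89% exact, 91% adjusted t |
| 4 vs 10, one-sided α 0.20 | about 80% (t 79.5%) | 93–95% |
| 10 vs 10, α 0.10 | 79% exact, 80% adjusted t, 82% t | 97–98% |

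More non-reactors cannot close the gap. With 4 reactors and a comparator mean known without error, δ → √4 = 2 and the power is Φ(2 − 1.282) = Φ(0.718) = 76%.

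The 10 vs 10 row matches the 80%. Those sizes fit SCD non-reactors against healthy controls, a comparison that contains no reactors. No reading tried returns 87% and 80% together.

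**Step 4: difference detectable with 80% power at 4 vs 10.** The exact test gives about 78.5% at 1.35 SD and 80.7% at 1.40 SD, so about 1.4 SD. The t-test reaches 80% at about 1.30 SD.

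**The case against.** The strongest objection is that 60% depends on normality. The plan names no distribution and chose a rank test because the scale of deposition is unknown. A rank test gains power for a shift of fixed SD when the data are heavy-tailed or skewed. Exact 4 vs 10 simulations at 1 SD give 63% for logistic errors, 68% for Laplace, 77% for exponential and 92% for lognormal with log-SD 1. So 80% at 1 SD is not impossible with 4 reactors.

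That stands as a reason to name the normal-shift assumption wherever the 60% is quoted. It does not rescue the sentence. The exponential and lognormal cases give 93% and 98% at 1.5 SD, not 87%. The shapes that stay near 87% at 1.5 SD (logistic 86%, Laplace 88%) give 63% and 68% at 1 SD.

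Two further points limit the finding. First, the 10 vs 10 origin of the 80% is a numerical match only; nothing in the plan confirms it. Second, Section 9.7 labels this work exploratory and optional, and the number of reactors is set by events already observed. Neither the primary endpoint nor its 27-subject sample size is touched.

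**Conclusion.** The concern holds. For 4 reactors against 10 non-reactors at one-sided 0.10, power at 1 SD is about 60% by the exact rank sum test and at most about 64% by the t-test benchmark, not 80%. The chance of missing a true 1 SD difference is about 40%, twice the stated 20%. The 87% at 1.5 SD is acceptable (about 85% exact).

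These values assume a normal shift with equal SDs, which is the assumption under which the plan's own 87% is recovered. The conclusion that the two figures do not belong to one comparison is firmer: every alternative tried for group size, significance level or error shape failed to return both. The importance is moderate. It affects how a null result on the first-listed secondary objective can be read, and nothing else in the trial.

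**What to change.** Replace the power sentence in Section 14.2 with wording such as:

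> With 4 SCD subjects with and 10 without a reaction, a one-sided 0.10 rank sum test has about 85% power for a 1.5 SD difference and about 60% for a 1 SD difference, assuming normal data with equal SDs; 80% power is reached at about 1.4 SD.

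If the 80% was intended for 10 SCD non-reactors against 10 healthy controls, keep it as a separate statement that names that comparison and its group sizes.

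The cost is one sentence and a less favourable power figure. No subjects, samples or analyses are added.
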